The study will use a randomized-experimental design and will be randomized via envelope randomization, with experimenters being blinded. A total of 104 patients, 26 in each group, will undergo initial incentive spirometry and force vital capacity (FVC) and FEV₁ tests. Groups will consist of a control versus experimental group, stratified into bilateral and unilateral rib fractures. Three days' worth of data will be collected for each of the tests and will also be collected 24 hours prior to discharge. Length of stays will be compared for experimental and control groups, as well as time to ambulation (collected from the first physical therapy assessment). Injury severity score will also be collected to determine any correlation by severity of injury. Patient satisfaction surveys for the device will also be collected to determine if the patients feel a difference with the device.

4) Background/Scientific Rationale and Significance

Little research as been conducted to determine the significance of a splinting device used in patients with chest trauma, and it is still uncertain whether these devices improve overall patient outcomes. Contradicting studies with similar experimental designs show either some significance (p-value) or insignificance in pulmonary function pre- and post-treatment. This gap in current knowledge leaves room for concern in whether the patient truly benefits from a splinting device in this type of injury. Changes in percent predicted FVC/FEV₁ ratio in this patient population are not readily demonstrated in most of these studies, as well as differing length of stays. This study will contribute to this base of knowledge by determining the effects of the Duracore splinting device on this patient population using the objectives.

5) Inclusion and Exclusion Criteria

Inclusion:

- Adult patient admitted to the trauma service at Penrose Hospital
- Willing and able to comply with all requirements of the study
- Active diagnosis of rib fractures
- Male or female ages 18 and older
- Able to provide written informed consent to participate in the study
- Must be physically able to don and use the splinting device independently without assistance

Exclusion:

- <18 years old
- History of pulmonary disease, lobectomy, or lung transplant
- Current smoker of tobacco products >5 years
- Diagnosis of flail chest

- Pregnant Women
- Prisoners
- Cognitively Impaired; must be alert and oriented x 3

6) Number of Subjects

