Number of subjects was based on a power analysis using FVC/FEV₁ as the primary variable and stratified by unilateral versus bilateral diagnosis. Previous literature suggests a standard deviation of approximately 0.20-0.60 for FVC/FEV₁ values. SD was set at 0.40. Unilateral control was estimated to be 50% of predicted values (FVC/FEV₁) due to the nature of the injury, set at approximately 1.50L, with bilateral set at approximately 1.35L. Unilateral experimental group means were increased by 20% of predicted values to 1.80L, and bilateral to 1.50L. The required sample size to achieve 80% power to detect difference between splint and control groups is 104, with each group requiring 26 subjects each. Power calculations were performed in R version 4.0.0 with the pwr2ppl package, using the anova2x2 function.

Number of subjects to be used are 150 to account for withdrawals, incomplete data sets, extraneous results, etc. This is a single site study.

7) Recruitment Methods

Respiratory Therapy is part of the trauma multi-disciplinary team. and is involved with the care of every trauma patient admitted to Penrose Hospital. During trauma rounds in the ICU and floor patients that met criteria for the study will be identified. The investigators will approach those identified patients for potential enrollment in the study. Note they will not approach any patient for consent that is under their care that shift. There are no flyers or advertisements for this research or device.

8) Study Timelines

It is estimated that it will take at least one year to complete this study to include enrollment, subject completion, and all analysis. All primary variables and analyses should be completed by this time.

9) Study Endpoints

The primary endpoint of this study is to investigate the use of the Duracore splinting device in patients with chest trauma. Hospital length of stays, time to ambulation, a patient satisfaction survey, incentive spirometry, forced vital capacity measurements, and the injury severity score will be correlated to a control group to determine its' effectiveness. The quantitative data points will be collected over the first three days of hospital stay and 24 hours prior to discharge. The qualitative data will be collected prior to patient discharge. The hypothesis of this study is that the use of the Duracore splinting device will reduce hospital length of stays and improve patient lung capacities over the course of admission following chest trauma.

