Data analysis will include a two-tailed t-test to account for significance between control and experimental groups. This will be done with both incentive spirometry and FVC/FEV₁. Correlations will be made with time to ambulation and length of stays, as well as injury severity score. Graphic representation of trends will also be used to demonstrate differences between the groups. Qualitative analysis will include providing averages from the questionnaire using a Likert scale. These averages will be used to determine whether the population felt the device provided any help with their chest trauma. Number of subjects was based on a power analysis

using FVC/FEV₁ as the primary variable. Previous literature suggests a standard deviation of approximately 0.20-0.60 for FVC/FEV₁ values. SD was set at 0.40. Unilateral control was estimated to be 50% of predicted values (FVC/FEV₁) due to the nature of the injury, set at approximately 1.50L, with bilateral set at approximately 1.35L. Unilateral experimental group means were increased by 20% of predicted values to 1.80L, and bilateral to 1.50L. The required sample size to achieve 80% power to detect difference between splint and control groups is 104, with each group requiring 26 subjects each. Power calculations were performed in R version 4.0.0 with the pwr2ppl package, using the anova2x2 function. Number of subjects to be used are 150 to account for withdrawals, incomplete data sets, extraneous results, etc. This is a single site study.

Patient satisfaction surveys will use a numbered Likert Scale. The averages of each answer will be used to reinforce the efficacy of the device and correlate to primary data. Randomization will occur by experimenter-blinded envelope randomization.

12) Provisions to Monitor the Data to Ensure the Safety of Subjects

Subjects will be monitored for the duration of their stay by all staff members, and any adverse events related to the device itself will be reported accordingly. This device claims minimal risk to patients due to its unrestrictive and non-invasive nature but will be monitored by investigators for any adverse effects. **The Data Safety Monitoring staff will review all documentation accordingly at least quarterly.**

13) Withdrawal of Subjects

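### Section 11 names only unspecified correlations for length of stay and time to ambulation; read as patient-level correlations with lung readings, they would not measure a splint effect

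*Combined protocol and SAP*

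**What the plan says.** Section 11 (Data Analysis Plan) opens with the test between groups: "Data analysis will include a two-tailed t-test to account for significance between control and experimental groups". It then limits the scope: "This will be done with both incentive spirometry and" FVC/FEV₁. The next sentence is all that section 11 offers for the two time outcomes: "Correlations will be made with time to ambulation and length of stays, as well as injury severity score". It does not state which variables form the pairs, whether the arms are pooled, or what is adjusted for.

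Two other sections bear on the same outcomes:

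- Section 9 (Study Endpoints) lists stay, ambulation, the survey, incentive spirometry, FVC and injury severity score (ISS), and says that they "will be correlated to a control group to determine its' effectiveness".
- Section 3 (Objectives and Hypothesis) says "Length of stays will be compared for experimental and control groups, as well as time to ambulation", with no test named. On severity it says "Injury severity score will also be collected to determine any correlation by severity of injury". No section plans an adjustment for ISS.

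The hypothesis, in sections 3 and 9, has two halves: shorter hospital stay and better lung capacity.

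**The concern.** Taken literally, section 11 examines stay, which is half of the hypothesis, only through correlations. Because the sentence follows directly on the lung readings, they are the likely partner variable. A lung reading and a length of stay are both measured after assignment, and both may depend on how badly the patient was injured. Patients with worse injuries may breathe less deeply, leave later and walk later in either arm. A negative correlation between reading and stay would then say something about injury and nothing about the splint. If such a result were cited beside section 9's reference to effectiveness, the stay hypothesis could appear supported without any comparison of the randomised groups.

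**Working it through.** **1. The plan's own figure.** Inputs from sections 6 and 11: control means 1.50 L (unilateral) and 1.35 L (bilateral), splint means 1.80 L and 1.50 L, SD 0.40, 26 per cell. Two-sided alpha of 0.05 is my assumption, since none is stated.

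- Splint main effect: [(1.80 - 1.50) + (1.50 - 1.35)] / 2 = 0.225 L.
- Noncentrality: 104 × (0.225/2)² / 0.40² = 8.23, F test on 1 and 100 df.
- Power: 81.1% at 26 per cell and 79.5% at 25 per cell.

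The stated 104 reproduces. It concerns a between-group comparison of a lung reading and says nothing about stay or ambulation.

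**2. The three sections side by side.** Section 3 compares stay and ambulation between groups but gives no method. Section 9 correlates them to a control group. Section 11 correlates them with unnamed partners. No section gives them an effect estimate, a confidence interval or a named between-arm test.

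**3. What a shared cause does to the correlation.** Assume no splint effect, severity correlated -a with the lung reading and +a with stay, and no other link. The induced correlation is (-a)(+a) = -a². The critical |r| at two-sided 5% is t/√(n - 2 + t²), which is 0.193 at n = 104 and 0.160 at n = 150 (the enrolment target). Results from 10,000 simulated trials per setting:

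| a | induced r | significant, n = 104 | significant, n = 150 |
|---|---|---|---|
| 0 | 0 | 5% | 5% |
| 0.2 | -0.04 | 7% | 8% |
| 0.3 | -0.09 | 15% | 20% |
| 0.4 | -0.16 | 37% | 50% |
| 0.5 | -0.25 | 73% | 87% |
| 0.6 | -0.36 | 97% | 99.5% |

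Hand check by Fisher's z at a = 0.5, n = 104: atanh(0.25) = 0.255; 0.255 × √101 = 2.57; Φ(2.57 - 1.96) = 0.73, which agrees.

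Making stay right-skewed lowers the rates only a little (14%, 32%, 66% and 94% at n = 104 for a = 0.3 to 0.6).

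**4. The same simulated data, other analyses.** Between-arm t-tests on the lung reading and on stay are significant in 4% to 5% of trials at every a. The correlation partialled on severity returns to about 5%, but only because severity is measured perfectly in the simulation. ISS would not achieve that.

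**5. What the documents say about a.** They give no correlation with severity. The nearest evidence is the pair of control means. With equal strata, each lies 0.15/2 = 0.075 L from their midpoint. The implied correlation of laterality with the reading is 0.075 / √(0.40² + 0.075²) = 0.075/0.407 = 0.18. If stay were linked to laterality equally strongly, the a = 0.2 row would roughly apply: 7% to 8% against a nominal 5%. Laterality is only part of severity, so a could be larger, but the documents do not say by how much.

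**The case against.** The strongest reply is that the plan never says what this point guards against. Section 11 does not name lung readings as the partner of stay and does not call its correlations proof of anything. A patient-level correlation cannot be computed to a control group, so section 9's phrase may be a loose way of promising a group comparison. Section 3 says outright that stay and ambulation will be compared. The lung readings have their own t-test, and severity does not bias that test if allocation is sound. The values of a are assumed, and the only documentary anchor points to the low end, where the excess over 5% is small.

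Most of this stands, and it limits the point. A reader might infer that the plan declares a lung-stay correlation to be evidence of effectiveness, or that severity alone does produce one, so that a useless splint should be expected to look supported. The documents support neither inference. The first joins section 9's wording to a different sentence in section 11. The second needs a value of a that is not given, and at a = 0.3 or 0.4 a significant result is still less likely than not at n = 104.

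The reply does not remove the gap. Section 3 names no test, and section 11, the section an analyst would follow, says correlations. Section 11 also intends survey averages to reinforce efficacy and to be correlated with the primary data, so the link between correlation and efficacy is not confined to one phrase.

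**Conclusion.** The point holds in a limited form. Sections 3, 9 and 11 do not agree on how stay and time to ambulation will be analysed, and section 11 followed literally gives them only correlations. If those are patient-level correlations with lung readings, they do not estimate a splint effect, whatever the value of a. How often they would mislead does depend on a: from about 7% (a = 0.2) to 97% (a = 0.6) at n = 104 with a null splint, assuming equal and opposite severity links and no other connection. The lung-reading t-tests are not undermined. What is at risk is any conclusion about stay or ambulation. The change is worth making because it costs little and affects what the trial can claim on half of its hypothesis.

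**What to change.** Reconcile sections 3, 9 and 11 as follows.

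- **Section 9:** state that effectiveness is judged only by comparing the groups as assigned, and replace the wording about correlating to a control group.
- **Section 11:** add a between-arm comparison of length of stay and of time to ambulation, each with an effect estimate and 95% CI, by a named method suited to skewed times and adjusted for the unilateral/bilateral stratum.
- **Section 11:** state which pairs of variables any correlations concern. Label those of lung readings with stay or ambulation exploratory and not evidence of a splint effect. If they are reported, adjust them for arm, stratum and ISS, and note that ISS captures severity incompletely.
- **Section 3:** refer to the analysis in section 11.

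All the variables are already on the collection list in section 9, and no patients are added. The cost is a little more analysis, and one favourable-looking result can no longer be cited as support.

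### Section 11 uses splint patients' satisfaction ratings to support efficacy without any between-arm analysis; these ratings can describe perceived help only

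*Combined protocol and SAP*

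**What the plan says.** Section 11 (Data Analysis Plan) gives the survey two uses. The first concerns perception: "These averages will be used to determine whether the population felt the device provided any help with their chest trauma". The second concerns efficacy: "The averages of each answer will be used to reinforce the efficacy of the device and correlate to primary data".

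The method offered is: "Qualitative analysis will include providing averages from the questionnaire using a Likert scale". On the instrument, section 11 says only: "Patient satisfaction surveys will use a numbered Likert Scale". The number of points, the anchors, the midpoint, and the wording and number of questions are not given.

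The between-group test in section 11 is a two-tailed t-test, and its scope is then set out: "This will be done with both incentive spirometry and FVC/FEV₁". The survey is not included.

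Other sections bear on the same point:
- Section 3: "Patient satisfaction surveys for the device will also be collected to determine if the patients feel a difference with the device".
- Section 9 includes the survey in the list used to judge effectiveness: "a patient satisfaction survey, incentive spirometry, forced vital capacity measurements, and the injury severity score will be correlated to a control group". No method follows. The section places collection of the qualitative data before discharge.
- Section 10: control patients receive standard care and no splint. The form is offered, not required, and carries no patient-identifying information.

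**The concern.** A rating of a device by the people using it reflects several things at once: any benefit of the device, natural recovery by the time of discharge, goodwill towards the staff and the study, and who chooses to fill in the form. Splint patients know that they have the splint. The plan speaks of blinded experimenters, but it describes no sham and no blinding of patients. An average taken in the splint arm alone cannot separate these components.

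That is harmless if the average is reported as what users said. It is not harmless once the average is declared to support efficacy. The plan as written would allow a trial with no difference in lung capacity to report favourable device ratings as reinforcing efficacy, although those ratings come from no randomised comparison.

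**Working it through.** **1. The plan's own figure.** The documents give no figure for the survey. Their only sample-size figure is 104 (26 per cell) for FVC/FEV₁. With cell means 1.50, 1.35, 1.80 and 1.50, SD 0.40 and an assumed alpha of 0.05, the treatment main effect is (0.30 + 0.15)/2 = 0.225. The noncentral F test in a balanced 2×2 design gives 79.5% power at 25 per cell and 81.1% at 26, so 104 is reproduced. It has no bearing on the survey except to fix the number of splint patients: 104/2 = 52, or 150/2 = 75 at the enrolment target.

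**2. Is there a usable comparison?** Section 11 gives the survey averages only and assigns the t-test to other variables. Section 9 names a control group without a method. Section 3 says that the survey is about the device, and section 10 says that controls do not get it. A comparison is therefore named, but it cannot be carried out on questions that only splint patients can answer.

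**3. How often would an ineffective splint look helpful?** No decision rule is written, so one has to be assumed: the splint-arm mean is above the scale midpoint. Let b be the true mean rating minus the midpoint when the splint has no effect (recovery, goodwill and similar), s the SD of a rating and n the number of raters. Then

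P(mean above midpoint) = Φ(b√n / s).

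With s = 1, n = 52 and b = +0.25, this is Φ(0.25 × 7.211) = Φ(1.803) = 96.4%.

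If instead the lower 95% limit has to exceed the midpoint,

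P = Φ(b√n / s − 1.96), which at b = +0.25 is Φ(−0.157) = 43.8%.

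| Lean b (points) | Mean above midpoint, n = 52 | Mean above midpoint, n = 75 | Lower 95% limit above midpoint, n = 52 | Lower 95% limit above midpoint, n = 75 |
|---|---|---|---|---|
| −0.25 | 3.6% | 1.5% | <0.1% | <0.1% |
| 0 | 50% | 50% | 2.5% | 2.5% |
| +0.10 | 76.5% | 80.7% | 10.8% | 13.7% |
| +0.25 | 96.4% | 98.5% | 43.8% | 58.1% |
| +0.50 | >99.9% | >99.9% | 95.0% | 99.1% |

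At n = 52 and b = +0.25, an SD of 0.8 gives 98.8% and an SD of 1.2 gives 93.3% for the mean rule. A simulated 1-to-5 scale with neutral opinion (10/20/40/20/10%) gives 47% instead of 50%, because some averages fall exactly on 3.

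**4. Reading.** The result depends almost wholly on b, which the documents do not give and which a one-arm survey cannot estimate separately from a device effect. A confidence limit deals with sampling error but not with b.

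**The case against.** Four points can be made for the plan.

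- **The survey is supportive only.** The sample size rests on FVC/FEV₁, the t-test covers spirometry, and the hypothesis concerns length of stay and lung capacity. This stands, and it limits the weight of the point.
- **The perception sentence is ordinary description.** Averaging ratings to say what patients felt is acceptable, and the wording allows a negative answer. This stands. A reader might infer that the survey can only ever come out in the device's favour, but the text does not say so. The difficulty lies in the sentence on efficacy.
- **Section 9 names a control group, and section 10 bars neither arm from the survey.** A reader might infer that no comparator was intended at all; section 9 contradicts that. What remains is that the comparison has no method and that device questions do not fit the control arm.
- **No error rate follows from the documents.** This also stands. A reader might infer that a splint with no effect would usually be judged helpful. That needs a decision rule, and the plan has none. Under the assumed midpoint rule, the chance is 50% at neutral opinion and about 4% at a lean of -0.25. Much higher figures result if one favourable question among several is taken to be enough, but no such rule appears in the plan.

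**Conclusion.** The point holds for the efficacy use of the survey. Ratings from unblinded splint patients, given voluntarily before discharge and analysed without a control value, are not evidence that the device works, and section 11 should not use them as such.

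The chance of a misleadingly favourable result is uncontrolled, not known to be high. It runs from about 4% to 96% as the no-effect lean goes from -0.25 to +0.25 points. That range assumes a midpoint rule, 52 splint patients, SD 1 and independent, roughly normal averages. Whether ratings lean positive is plausible but assumed. The missing scale, cut-off and interval are gaps in detail and secondary to the claim of efficacy. The change is worth making because it affects what the trial may conclude, but the sample size and the spirometry analysis do not depend on it.

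**What to change.** In section 11:

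1. Delete the statement that the averages reinforce efficacy. State that device ratings describe perceived help only and that conclusions on efficacy rest on the randomised between-arm comparisons.
2. Give the scale, anchors and questions. Report splint-arm ratings with the full response distribution, a 95% confidence interval for the mean, and the response rate.
3. If the survey is to support effectiveness as section 9 says, ask both arms one question that applies to both, put an arm code on the form, and report the between-arm difference with a 95% confidence interval. With 52 per arm and an assumed SD of 1, the half-width is about 1.96 × √(2/52) = 0.38 points. Randomisation then balances natural recovery. Goodwill from knowing one has the splint is not removed and should be named as a limitation.
4. Either drop the planned correlation of ratings with primary data or say how forms will be linked. An arm code is not enough for that; a study code would be needed and would have to be reconciled with the anonymity promised in section 10.

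Items 1 and 2 cost a change of wording and one interval, with no new patients or procedures. Item 3 adds one question and a code to the form. The downside is small: favourable device ratings can no longer be cited as support for efficacy.

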Variables to be collected are:

- Age (years)
- Gender
- Diagnosis

CHI Institute for Research and Innovation

- Incentive Spirometry values for this admission
- FVC/FEV1 values for this admission
- Height, Weight, and Ethnicity for FVC/FEV₁ % predicted calculation
- Averages from the patient satisfaction survey using a Likert Scale
- Length of Stays
- Time to Ambulation
- Injury Severity Score

10) Procedures Involved

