The design of this study is a randomized experimental trial. The procedures involved in this study will first include obtaining the individual's consent to participate. Incentive spirometry is a standard of care that has been proven to improve deep breathing for patients. FVC/FEV₁ measurements are not always routinely done at this site but has been proven to be an indicator in respiratory deterioration in this population. Enrollment of each subject will be on a one to one basis for control and experimental groups. The trial will be randomized to reduce bias by randomly selecting patients between control and experimental groups by alternating every other patient receiving the treatment. Height, sex, ethnicity, and age will be accounted for as well to calculate the percent predicted FVC/FEV_1 to reduce statistical error. Enrollment will be based on patient consent. After enrollment into the study after admission to the hospital, baseline values of incentive spirometry (IS) and spirometry will be done. The patient will then be placed in the experimental or control group after being assigned a group via envelope randomization. If the patient is under experimental, they will receive a splinting device for treatment. Control groups will receive standard of care treatment without the splinting device. Continued analysis of IS and FVC/FEV₁ will occur over three days, and a final collection prior to discharge. Discharge planning will be coordinated with respiratory therapy, so the patient does not go home without completing the survey and final analysis. The patient satisfaction survey will be a paper survey administered to the patient. Patient identifying information will not be present on this form to maintain confidentiality. The patient will be asked if they would like to complete the form and that it is an anonymous short survey to help with identifying how the patient felt about the research. The subject will only be enrolled in the study for the duration of their hospital stay as an inpatient. There will be no follow-up after discharge, and any patients who are discharged without completing the final analysis will be omitted from the study.

11) Data Analysis Plan

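### Survey averages are meant to support efficacy and be correlated with the primary data, but the anonymous form has no described link to patient or arm, and perceived help is not efficacy evidence

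*Combined protocol and SAP*

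**What the plan says.** **Use of the survey.** Section 11 (Data Analysis Plan) says: "The averages of each answer will be used to reinforce the efficacy of the device and correlate to primary data". It also says: "These averages will be used to determine whether the population felt the device provided any help with their chest trauma". Section 9 (Study Endpoints) names the survey among measures to be set against control in judging effectiveness: "a patient satisfaction survey, incentive spirometry, forced vital capacity measurements, and the injury severity score will be correlated to a control group". The variable list in the same section records "Averages from the patient satisfaction survey using a Likert Scale", without saying whether the average is per patient, per item or per arm.

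**The form.** Section 10 (Procedures Involved) says of the paper survey: "Patient identifying information will not be present on this form to maintain confidentiality". Patients are told that "it is an anonymous short survey to help with identifying how the patient felt about the research". Neither a study number nor an arm label is mentioned.

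**Who answers.** Section 3 says: "Patient satisfaction surveys for the device will also be collected to determine if the patients feel a difference with the device". Section 10 says: "Control groups will receive standard of care treatment without the splinting device". It then describes the survey for the patient in general, without limiting it to one arm.

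**Completion.** Section 10 has discharge coordinated so that no patient leaves with the survey undone. A few sentences later it has the patient asked whether they wish to fill it in.

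**The concern.** Two uses are planned for the survey, and the design described supports neither.

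The first is correlation with the primary data. A patient-level correlation needs each score paired with that patient's outcomes. The only description of the form is of an anonymous one, and no pairing key is given.

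The second is support for efficacy. Device patients put the device on and operate it themselves, so they know what they received. Their opinion of whether it helped can reflect expectation as well as effect. Controls have no device to rate, so a device rating has no natural control counterpart. If only device patients answer, there is no control comparison at all.

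At stake is what the report may claim. Opinions from patients who know their treatment could be presented as backing for efficacy, and a correlation could be reported that the data as described cannot supply.

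**Working it through.** The plan gives no figure for the survey, so the main check is a comparison of the text.

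**1. Is the survey part of the sample size?** Section 6 takes 26 per cell (104 in all) from FVC/FEV₁ means of 1.50 and 1.35 (control) and 1.80 and 1.50 (device), with SD 0.40. The average device effect is (0.30 + 0.15)/2 = 0.225. For the splint main effect in a 2×2 ANOVA, the noncentrality is 104 × (0.225/2)² / 0.40² = 8.23 on 1 and 100 degrees of freedom. At two-sided alpha 0.05 (assumed, as none is stated) power is 81.1%; 25 per cell gives 79.5%. So 104 reproduces, and no survey quantity enters it.

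**2. Is a link described?** Three places bear on this.
- Section 10: no identifying information on the form; the patient is told it is anonymous.
- Patient Confidentiality and Disclosure: eCRF data are also called anonymous, yet carry an enrollment number and initials. The survey form is not named.
- Retention of Documents: case report form data must be traceable to source. The survey form is again not named.

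In this protocol, then, anonymous does not exclude a code, but no code is stated for the survey.

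**3. What could be correlated under each arrangement?** The following is illustrative, with two-sided alpha 0.05, 80% power and every form returned (all assumed).
- No key: no pairs, so no patient-level correlation.
- Arm known only: two pairs of averages. Two points give r = +1 or −1 whatever the data, unless values tie.
- Arm and stratum known: four pairs. The critical value is |r| = t/√(2 + t²) with t = 4.303 on 2 degrees of freedom, which is 0.95.
- Study number, device patients only (52): detectable r = tanh((1.960 + 0.842)/√49) = 0.38.
- Study number, both arms (104): detectable r = tanh((1.960 + 0.842)/√101) = 0.27.

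Only a study number gives a usable correlation, and who answers changes what it can show.

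**4. Can the ratings support efficacy?** The inclusion criteria (section 5) require patients to don and use the device unaided, and section 10 gives controls none. The blinding in sections 3 and 11 is of experimenters, so it does not stop a patient knowing whether they have the device. The documents give no way to size the resulting bias.

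**5. Is completion required or optional?** The two statements in section 10 conflict, so the expected return cannot be read from the plan.

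**The case against.** The strongest reply is that the plan uses the word correlate loosely. Section 9 has measures correlated to a control group, which can only mean compared. Section 11 speaks of averages of each answer and section 9 lists only averages, so neither requires a score per patient. If the averages are simply to be shown beside the results, no link is needed. This has force, but it leads to a wording change: a side-by-side display should not be called a correlation.

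A second reply is that the survey is called qualitative, that no test or decision rule uses it, and that its role is only supportive. That is true and keeps the point minor. It does not make opinions from patients who know their treatment into efficacy support.

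Two stronger readings are tempting and are not supported.
- A reader might infer that scores cannot be paired with patients at all. The survey form is not in the available text, the consent pages were removed, and the protocol calls numbered eCRF records anonymous. The documents support only that no link is described.
- A reader might infer that the reported average will be diluted by control patients' answers. That needs both arms to answer, the forms to be unlabelled and the forms to be pooled. Sections 3 and 11 point more towards device users, in which case there is no dilution. Section 9 and the unrestricted wording of section 10 leave the other reading open, but no dilution figure can be given.

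Uncertainty over who answers would, by itself, be only missing detail. It matters here because it decides whether any control comparison exists.

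**Conclusion.** The concern holds in a limited form. The plan assigns the survey an efficacy role and a correlation, while describing an anonymous form with no study number or arm label. As described, a patient-level correlation has no data link, and perceived help from patients who know they have the device is not efficacy evidence. The plan also contradicts itself on whether completion is optional.

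This is a minor, secondary issue. It limits what may be concluded from the survey and leaves the FVC/FEV₁ comparison and the sample size untouched. The conclusion rests on the published text; a code printed on the actual form would settle the link, but not the efficacy wording or the conflict over completion.

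**What to change.** In section 11, delete the statement that the averages support efficacy. Report them descriptively as perceived benefit or acceptability, with forms returned out of forms offered. State which arm or arms receive the form. In section 10, state that completion is voluntary and remove the conflicting wording.

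Then choose one option before data collection:
- **(a)** Keep the form anonymous and delete the correlation with primary data. If both arms answer, add an arm code that staff described as blinded cannot read; a plain arm label could reveal allocation around the time of the final spirometry.
- **(b)** Print the study number on the form, describe it to patients as coded and confidential, and label any patient-level correlation exploratory.

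If forms have already been collected, the efficacy and correlation claims can still be dropped.

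**Cost.** Either option needs a written amendment approved by the responsible party and the IRB. Option (a) gives up the patient-level link. Option (b) changes what patients are told and may make answers less candid.
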